#### 8.2. Patient Exclusion Criteria

All patients with any of the following conditions or characteristics must be excluded from the study:

- Prior exposure to bardoxolone methyl;
- Kidney or other solid organ transplant recipient or a planned transplant during the study;
- 3. B-type natriuretic peptide (BNP) level >200 pg/mL at Screen A visit;
- Acute dialysis or acute kidney injury within 12 weeks prior to Screen A visit or during Screening;
- Serum albumin < 3 g/dL at Screen A visit;

- 6. Systemic immunosuppression for more than 2 weeks, cumulatively, within the 12 weeks prior to randomization or anticipated need for immunosuppression during the study. Patients with IgAN or FSGS that are receiving prednisone at doses ≤ 10 mg/day are eligible for enrollment in the IgAN or FSGS cohorts, but doses must be stable for 30 days prior to Screen A visit and should be anticipated to remain the same throughout the study. Refer to Section 9.3.1 for additional details;
- For patients enrolling in IgAN Cohort:
  - Systemic manifestations of Henoch-Schonlein purpura within 1 year prior to Screen A visit;
  - Have used belimumab, eculizumab, or rituximab within 6 months prior to Screen A visit;
- For patients enrolling in ADPKD Cohort:
  - Receiving tolvaptan;
- Cerebrovascular event (stroke, transient ischemic attack) or aneurysm within 6 months prior to Screen A visit or during Screening;
- 10. History of clinically significant left-sided heart disease and/or clinically significant cardiac disease, including but not limited to any of the following:
  - Clinically significant congenital or acquired valvular disease;
  - b. Left ventricular ejection fraction < 40% (based on echocardiogram performed at Screen A visit or within 6 months prior to Day 1);
  - Pericardial constriction (based on echocardiogram performed at Screen A visit or within 6 months prior to Day 1);
  - Restrictive or congestive cardiomyopathy (based on echocardiogram performed at Screen A visit or within 6 months prior to Day 1);

- e. Symptomatic coronary disease (prior myocardial infarction, percutaneous coronary intervention, coronary artery bypass graft surgery, or angina);
- History of hospitalization for heart failure;
- g. Cardiac insufficiency, defined as New York Heart Association Class >2;
- History of atrial fibrillation;
- History of unstable arrhythmias;

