# 9.10.5. Medical History

A complete medical history (e.g., per patient report) that includes all medical history within the past 5 years must be collected. Medical history will be recorded as indicated in Table 5.

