11.2.2. Historical eGFR Slope Dataset

Up to 5 years of historical serum creatinine values will be collected for each patient as part of their medical history information. Serum creatinine values will be converted to mg/dL and eGFR will be calculated according to the equations in 7.1.3 using the patient age at laboratory collection. Historical serum creatinine values will have been analyzed at various local laboratories (i.e., not collected as part of central lab data). Historical serum creatinine values will be converted to mg/dL if not entered in those units. Therefore, historical serum creatinine and eGFR values will be treated separately from data collected as part of the trial's central lab assessments.

One dataset will be generated with the baseline eGFR values, baseline log(ACR) values, the historical eGFR values, and the eGFR results in PHOENIX that were used in the primary efficacy analysis (Section 7.3 and Section 11.1). The analysis time points are defined as follows:

Table 5: Comparison of eGFR Slope in PHOENIX vs. Historical eGFR Slope

Analysis Time Point	Study Day Windows
Historical	1825 to 1 days prior to Screen A
Baseline	Screen A to Day 1
On Treatment	Day 2 to Day 98

The eGFR values used in the analysis datasets for the baseline label will be the baseline eGFR values for each patient (defined in 7.2.1), not the individual Screen A, Screen B, and Day 1

eGFR values. The continuous year will be calculated as a continuous variable as Study Day / 365.25. Historical values will have a negative Study Day value, calculated as Date of Lab Collection – Date of Day 1 Study Day. Week 16 values will not be included in the analysis. Baseline eGFR values will have a continuous year value of zero.

A separate dataset will be generated for summary statistics of historical and on-treatment results, for patients with historical eGFR data entered. The second date will separate the historical and on-treatment results by year to calculate summary statistics, but will not be used in the statistical model described in Section 11.2.3.

Table 6. Labels for Summary of Historical and On-Treatment Change in eGFR

Label	Study Day Windows
Historical Year 5	Day -1825 Before Screen A to Day -1461 Before Screen A
Historical Year 4	Day -1460 Before Screen A to Day -1096 Before Screen A
Historical Year 3	Day -1095 Before Screen A to Day -731 Before Screen A
Historical Year 2	Day -730 Before Screen A to Day -366 Before Screen A

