Historical Year 1	Day -365 Before Screen A to Day -1 Before Screen A
Baseline	Day -60 to Day 1
Year 1	Day 2 to Day 98

The summary statistics will include the average GFR value by patient and analysis time point. For instance, if multiple values are listed in the year 1 results for a given patient, the average of those values will be used to calculate the summary statistics. However, all eGFR values will be used in the statistical model described in Section 11.2.3.

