11.2.3. Statistical Model

The general linear model will be run according to the year labels in Table 5.

The table summaries will report the historical change in eGFR vs. baseline (with no post-baseline eGFR values from PHOENIX in the model), and the change in eGFR vs. baseline on bardoxolone methyl treatment for patients who have historical serum creatinine values reported.

Only patients at least one historical eGFR value entered will be included in the analysis.

The change in eGFR will be analyzed by an analysis of covariance, with baseline eGFR and natural log(Baseline ACR) as covariates:

[REDACTED]

[REDACTED]

The LSMeanDiffCL will compare historical eGFR slopes and eGFR slope in PHOENIX along with appropriate confidence intervals, and the Diff results will provide the appropriate p-values. Results will be summarized by cohort.

Summary statistics of the datasets listed in [Table 5](#) by analysis time point will also be summarized.

All historical eGFR data will be listed.

[REDACTED]

[REDACTED]

[REDACTED]

[REDACTED]

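### SAP Table 6 averages the eGFR level each historical year over whoever has a value that year, so the descriptive five-year trend can reflect who has records instead of change within patients

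*SAP*

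**What the plan says.** **Source of the data.** SAP 11.2.2: "Up to 5 years of historical serum creatinine values will be collected for each patient as part of their medical history information". It adds: "Historical serum creatinine values will have been analyzed at various local laboratories". Protocol 9.10.5 describes the underlying collection: "A complete medical history (e.g., per patient report) that includes all medical history within the past 5 years must be collected". Neither document sets a minimum number of creatinine values, a spacing, or a requirement that every year be covered.

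**Who enters.** SAP 11.2.3: "Only patients at least one historical eGFR value entered will be included in the analysis". The separate by-year dataset is likewise built "for patients with historical eGFR data entered".

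**What is summarised.** Table 6 has five historical rows of 365 days each, a Baseline row, and an on-treatment row covering Day 2 to Day 98. The operative sentence is "The summary statistics will include the average GFR value by patient and analysis time point". Several values from one patient in one row are averaged first. The statistic is the eGFR level, although the title of Table 6 speaks of change in eGFR.

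**Standing of the table.** It is descriptive. SAP 11.2.2 says that the by-year dataset separates results by year "but will not be used in the statistical model described in Section 11.2.3". SAP 7 makes the number of patients with data a default statistic, and SAP 11.2.3 has all historical eGFR data listed.

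**The concern.** The trial has one arm and no comparator, so a patient's eGFR before the study is its only view of the untreated course. A reader will look down the Table 6 rows for that course. Each row, however, is a mean level over the patients who happen to have a value in that year. If patients with long records had systematically higher or lower eGFR than those with short records, the row means would drift from Year 5 to Year 1 as shorter-record patients joined, with no change in any individual. A real decline could be exaggerated, masked or invented.

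At stake is how the pre-study trend is read, not the test of the drug. SAP 3 allows the planned analyses to go into regulatory submissions and manuscripts, so the table may be seen outside the study report.

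**Working it through.** **The plan's own figure.** None is stated for this table. The 80% power in SAP 6 concerns the primary endpoint and has no bearing here.

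**Inputs.** From the documents: about 25 patients per cohort; screening eGFR 30 to 90 mL/min/1.73 m²; entry on one historical value. Assumed, because the documents do not give them: the share of patients with a value in each year, and the level difference between long- and short-record patients.

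**Step 1. Drift with no true slope.** Assume coverage of 40, 50, 65, 80 and 95% for Years 5 to 1, with nested records (a patient with a value in one year also has one in each later year). Let the 40% with full records differ by D = 10 from the rest. The shift in a row mean is D × 0.40 / coverage:

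| Row | Coverage | Shift |
|---|---|---|
| Year 5 | 0.40 | 10.0 |
| Year 4 | 0.50 | 8.0 |
| Year 3 | 0.65 | 6.2 |
| Year 2 | 0.80 | 5.0 |
| Year 1 | 0.95 | 4.2 |

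The apparent change from Year 5 to Year 1 is 4.2 − 10.0 = −5.8 if long-record patients have the higher eGFR, and +5.8 if they have the lower.

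**Step 2. Drift on top of a true slope.** With −3 per year, the true change from Year 5 to Year 1 is 4 × (−3) = −12. The table would show −12 − 5.8 = −17.8 or −12 + 5.8 = −6.2.

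**Step 3. Range.** In general a row mean differs from the mean of all patients by (1 − p) × d, where p is the share with a value and d is the mean of those with a value minus those without. For d from 5 to 15 this is 1 to 3 at p = 0.8, 2 to 6 at p = 0.6, and 3 to 9 at p = 0.4. At full coverage it is zero.

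**Step 4. Chance alone.** If record length is unrelated to eGFR there is no bias, but small cohorts still move. Taking a between-patient SD of 17 (a uniform spread over 30 to 90 gives 60/√12 = 17.3), the membership error of a row mean is 17 × √(1/(25p) − 1/25). This is 1.7 at p = 0.8, 2.8 at p = 0.6 and 4.2 at p = 0.4.

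**Step 5. Does change from own baseline cure it?** A simulation used 25 patients and 4,000 runs, with baseline uniform on 30 to 90, true slope −2 per year, between-patient slope SD 1.5, and coverage falling from 90% in Year 1 to about 30% in Year 5. The trend is a straight line through Baseline and the yearly rows.

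| Record length | Row means as planned | Change from own baseline |
|---|---|---|
| Longer in low-eGFR patients | −0.1 | −2.0 |
| Unrelated to eGFR | −2.0 (SD 1.3) | −2.0 (SD 0.6) |
| Longer in high-eGFR patients | −3.9 | −2.0 |

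With about 90% coverage in every year, both versions give −2.0 with SD 0.4.

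**Step 6. Effect at baseline.** If the 5% without a Year 1 value stay in the Baseline row, its shift is 10 × 0.40 = 4.0, against 4.2 in Year 1, a step of 0.2. Under nested records those patients have no historical value at all and drop out, so the step is zero.

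**The case against.** The best defence is that this is a descriptive table, that N per row would reveal thin early years, that every historical value is listed, and that the title already promises change. SAP 11.2.3 also reports historical change against baseline, adjusted for baseline eGFR and log ACR. The descriptive status stands and limits the weight of the point. The rest does not remove it. N shows that membership changed, but not which way or how far the mean moved. The adjusted change in 11.2.3 is run on the Table 5 labels, not the yearly rows. For Table 6 the operative sentence averages the level, and a title does not override it.

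Four stronger readings are tempting, and the documents do not support them.

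- **That historical tests were prompted by illness.** No section says why they were drawn. That patients differ from year to year is likewise permitted by the plan, not stated.
- **That on-treatment eGFR covers everyone.** The by-year summary is limited to patients with historical data, and SAP 11.1 drops values after discontinuation.
- **That data collection changes when the drug starts.** Historical values end before Screen A. Baseline under SAP 7.2.1 already uses central-laboratory screening and Day 1 values. The switch lies between Historical and Baseline, so the 5.8 should not be set against the on-drug gains quoted in the protocol.
- **That historical acute kidney injury values should be removed to mirror the entry rule** (Protocol 8.2: "Acute dialysis or acute kidney injury within 12 weeks prior to Screen A visit or during Screening"). This would filter the historical side only, raise the historical mean and steepen the apparent decline, which favours the drug. It also needs dated episodes that a history by patient report may not supply.

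**Conclusion.** The point holds for the descriptive Table 6 trend. As written, SAP 11.2.2 lets the row means move with membership, by 5.8 mL/min/1.73 m² between Year 5 and Year 1 in the illustration and by anything from nothing to more than that under other assumptions. The size rests wholly on assumed coverage and an assumed level difference. With nearly complete records the problem disappears.

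The primary endpoint (Week 12 change against zero) is untouched. So is the model on the Table 5 labels, which does not use the yearly rows; its code is redacted, and nothing is claimed here about how it handles repeated values. The baseline-to-on-treatment change is also unaffected, because both rows come from the patients with historical data regardless of how long their records are.

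This is a modest defect in a supporting table, worth correcting because the better summary needs no new data.

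**What to change.** In SAP 11.2.2, replace the averaging of the eGFR level with this rule: for each Table 6 row, average the values within patient, subtract that patient's baseline eGFR as defined in SAP 7.2.1, and summarise the differences. Report the number of patients and the number of values in each row. This brings the text into line with the table's title. Optionally, repeat the table in patients who have a value in every year shown.

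The cost is a change of SAP wording and, with the optional repeat, one extra table. Its numbers would be small: at the assumed 40% coverage in Year 5, 0.40 × 25 = 10 patients per cohort.

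The limits should be stated with the table. The change removes differences in level between long- and short-record patients, but not differences in slope. It does not correct for tests that may have been drawn during illness: in the same simulation, with 10 to 30% of tests falling in a dip of 5 to 15 mL/min/1.73 m², both versions moved from −2.0 to between −1.9 and −1.4 per year. Historical change also runs from local to central laboratories, as it already does in SAP 11.2.3.

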11.2.3. Statistical Model

The general linear model will be run according to the year labels in Table 5.

The table summaries will report the historical change in eGFR vs. baseline (with no post-baseline eGFR values from PHOENIX in the model), and the change in eGFR vs. baseline on bardoxolone methyl treatment for patients who have historical serum creatinine values reported.

Only patients at least one historical eGFR value entered will be included in the analysis.

The change in eGFR will be analyzed by an analysis of covariance, with baseline eGFR and natural log(Baseline ACR) as covariates:

[REDACTED]

[REDACTED]

The LSMeanDiffCL will compare historical eGFR slopes and eGFR slope in PHOENIX along with appropriate confidence intervals, and the Diff results will provide the appropriate p-values. Results will be summarized by cohort.

Summary statistics of the datasets listed in [Table 5](#) by analysis time point will also be summarized.

All historical eGFR data will be listed.

[REDACTED]

[REDACTED]

[REDACTED]

[REDACTED]

11.3. Sensitivity Analyses

The primary analysis method (MMRM) uses all available data, and assumes data are missing at random. A tipping point analysis or other sensitivity analyses may be performed as appropriate.

12. SAFETY ANALYSES

Safety and tolerability are evaluated by AEs, SAEs, clinical laboratory test results, body weight, vital signs, 12-lead ECG findings, physical examination, visual acuity, and audiology assessment. All analyses of the safety data will be performed using the safety analysis set. Descriptive statistics (described in Section 7) will be presented for the safety analysis set.

12.1. Adverse Events and Serious Adverse Events

All adverse event verbatim terms on eCRFs will be mapped to preferred terms and system organ classes using the Medical Dictionary for Regulatory Activities (MedDRA[®]) Dictionary (version 14.1).

12.1.1. Treatment Emergent Adverse Events

Treatment-emergent AEs (TEAEs) are defined as any AEs, regardless of relationship to study drug, that have an onset or worsen in severity on or after the first dose of study drug and not more than 30 days after the date of the last dose of study drug. If it cannot be determined whether the AE is treatment-emergent due to a partial onset date, then it will be counted as a TEAE. Adverse events with incomplete start dates will be considered TEAEs, if:

- Onset time is missing but the onset date is on Study Day 1.
- Day and month are missing and the year is equal to or after the year of the first date of study drug dosing;
- Day is missing and the year is after the year of the first date of study drug dosing;

- Day is missing and the year is equal to the year of the first date of study drug dosing and the month is equal to or after the month of the first date of study drug dosing; or
- Year is missing.

Related AEs are those with relationship to study drug reported as “possibly related”, “probably related”, or “definitely related”. If severity (relationship to study drug) of an AE to study drug is not recorded, the severity (relationship to study drug) will be imputed as ‘severe’ (‘definitely related’).

All reported AEs (including non-TEAEs), SAE, and deaths will be listed in separate patient listings.

12.1.2. Summary of Treatment-Emergent Adverse Events and Serious Adverse Events

TEAE and SAE presentations will summarize results by rare CKD cohort. All TEAE summary tables will include the number and percentages of patients reporting TEAEs. A summary of TEAEs by severity, seriousness, and relation to study drug will be tabulated. In addition, TEAEs will be summarized by MedDRA system organ class and preferred term. These summaries will include the following:

- All TEAEs
- TEAEs by worst severity
- Related TEAEs
- TEAEs leading to study drug interruption (if any)
- TEAEs leading to study drug discontinuation (if any)
- All treatment-emergent SAEs
- Treatment-emergent SAEs by worst severity
- Related treatment-emergent SAEs.

At each level of patient summarization, a patient is counted once if he/she reported one or more TEAE at that level. If a patient reported the same TEAE on multiple occasions, the highest severity (severe > moderate > mild) or study drug relationship (related > probable > possible > unlikely > unrelated) recorded for the event will be summarized. Each summary will be ordered by descending order of incidence of system organ class and preferred term within each system organ class.

12.2. Clinical Laboratory Evaluation

Clinical laboratory test (serum chemistry [including NT-Pro BNP, BNP, IGF-1 and serum ketones], hematology [including hematocrit, hemoglobin (Hgb), red blood cell (RBC) count, white blood cell (WBC) count, neutrophils, bands (if detected), lymphocytes, monocytes, basophils (if detected), eosinophils (if detected), absolute platelet count, mean corpuscular hemoglobin (MCH), mean corpuscular volume (MCV), and mean corpuscular hemoglobin concentration (MCHC)], spot urine, and urinalysis of pH and specific gravity) results from the

central laboratory, where available, will be summarized by rare chronic kidney disease cohort using descriptive statistics at each scheduled time point. Laboratory assessments below LLD will be imputed as LLD/2. Laboratory assessments above the ULD will be imputed as the ULD. Changes from baseline will also be summarized by time point. Summaries of ACR will use the geometric mean with 95% confidence intervals instead of the arithmetic mean, and will display ACR results in units of mg/g. Changes from baseline in ACR will be reported as the post-baseline/baseline ratios and will be summarized by geometric means with 95% confidence intervals at each time point. Mean ratios of natural log(ACR)/eGFR will also be summarized at each time point. The ratio of natural log(ACR)/eGFR by analysis visit will be summarized by arithmetic means. Box plot graphs and line graphs may be generated for selected laboratory tests, such as ACR, ALT, AST, BUN, uric acid, magnesium, and creatinine. Line graphs will include mean \pm SE over time for both the observed values and for the change from baseline values.

Additional summary tables will be provided that includes that number and percentage of patients meeting the following 1) pre-specified threshold level at any time during the study (Table 7) and 2) ULN thresholds at any time during the study (Table 8).

Table 7: Pre-Specified Threshold Levels for Categorical Laboratory Summaries

Lab Parameter	Pre-Specified Level
ACR	> 3500 mg/g
Magnesium	< 1.3 mEq/L (0.65 mmol/L)
BNP	> 200 pg/mL
ALT, AST	> 3 \times upper limit of normal (ULN)
ALT, AST	> 8 \times ULN
ALT, AST	> 5 \times ULN for more than 2 weeks
ALT, AST, TBL, INR	> 3 \times ULN and (TBL > 2 \times ULN or INR > 1.5 \times ULN)

Table 8: Pre-Specified Upper Limit of Normal (ULN) Levels for Laboratory Parameters

Lab Parameter	Sex	Age	ULN
ALT	Female	All	34 U/L
	Male	All	43 U/L
AST	Female	< 18	40 U/L
		\geq 18	34 U/L
	Male	< 18	40 U/L
		\geq 18	36 U/L
TBL			Central lab ULN
INR			Central lab ULN

Urinalysis results other than pH and specific gravity will not be summarized. Results not summarized include of ketones, protein, blood, glucose, clarity, color, leukocytes, nitrite,

bilirubin, and microscopic examinations (if indicated based on laboratory results), urine microscopic findings, and pregnancy test results will not be summarized.

Laboratory results that are above or below normal limits will be flagged in the listings.

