## 5.1.2.5. Hypomagnesaemia

Hypomagnesaemia has not been reported in PH patients to date, but was reported as an AE for 15.5% of patients with CKD who also had type 2 diabetes who received bardoxolone methyl. The AE of hypomagnesaemia (of any reported relationship to study drug) was more frequently reported in bardoxolone methyl-treated patients than in patients given placebo. The investigators considered almost all reported events to be mild. Additionally, patients treated with bardoxolone methyl had a greater decrease from baseline in serum magnesium levels than patients given placebo; the decrease was evident within 4 weeks and attenuated after 8 weeks of starting therapy. In bardoxolone methyl clinical studies performed to date, a post-hoc analysis identified no correlation between hypomagnesaemia and either gastrointestinal AEs or cardiac AEs, including cardiac dysrhythmias and prolonged QTc. The 24-hour urine collections from the BEACON ambulatory blood pressure monitoring sub-study showed no increase in urinary magnesium levels, indicating that renal loss of magnesium did not account for the reductions in serum magnesium observed with bardoxolone methyl treatment in CKD patients. Notably, a thorough QT study that tested doses of bardoxolone methyl up to 80 mg, bardoxolone methyl showed no increase in the QT interval.

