### 9.1.5. Hypomagnesaemia

In instances where a patient experiences hypomagnesaemia, defined as serum magnesium less than 1.3 mEq/L (0.65 mmol/L), consideration should be given to repletion of serum magnesium.

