# 9.10.20. Clinical Chemistry

Samples will be collected for the following clinical chemistry analyses as indicated in Table 5: ferritin, creatine kinase (CK), BUN, enzymatic creatinine, eGFR, TBL, direct bilirubin, ALT, AST, ALP, sodium, potassium, calcium, phosphorus, uric acid, total protein, glucose, albumin,

lactate dehydrogenase (LDH), magnesium, chloride, bicarbonate, and GGT. Women of childbearing potential will require a serum pregnancy test (hCG-Qual) at the Screen A visit or at any point in time if a pregnancy is suspected.

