# 11.2. Adverse and Serious Adverse Events

### 11.2.1. Definition of Adverse Events

### 11.2.1.1. Adverse Event

An AE is defined as any untoward medical occurrence in a patient regardless of its causal relationship to study drug. An AE can be any unfavorable and unintended sign (including any clinically significant abnormal laboratory test result), symptom, or disease temporally associated with the use of the study drug, whether or not it is considered to be study-drug related. Included in this definition are any newly-occurring events or previous condition that has increased in severity or frequency since the administration of study drug.

All AEs that are observed or reported by the patient during the study (from time of administration of the first dose at the Day 1 visit until the final visit indicated in Table 5 must be reported, regardless of their relationship to study drug or their clinical significance.

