5.3. Assessments

All patients in the study will follow the same visit and assessment schedule. Table 2 lists the overall schedule of assessments for the study. Following randomization on Day 1, patients will be scheduled for assessments during treatment at Weeks 1, 2, 4, 6, 8, and 12, and by telephone contact on Days 3, 10, 21, 31, 38, and 45. Patients will also be scheduled for an in person follow-up visit at Week 16, four weeks after the end of treatment.

Table 2: Schedule of Assessments

Assessment	Screen A ^a	Screen B ^b	Day 1 ^c	Wk 1 (Phone) Day 3±2	Wk 1 Day 7±3	Wk 2 (Phone) Day 10±2	Wk 2 Day 14±3	Wk 3 (Phone) Day 21±2	Wk 4 Day 28±3	Wk 4 (Phone) Day 31±2	Wk 5 (Phone) Day 38±2	Wk 6 Day 42±3	Wk 7 (Phone) Day 45±2	Wk 8 Day 56±3	Wk 12 or EoT ^d Day 84±3	Wk 16 or F/U Day 112±3
Informed consent	X															
Inclusion/ exclusion	X		X ^e													
Demographics and baseline disease characteristics	X															
Concomitant medications	X	X	X	X	X	X	X	X	X	X	X	X	X	X	X	X
Medical history	X															
Height	X															
Weight in clinic/BMI	X		X		X		X		X			X		X	X	X
Weight at home			X	X	X	X	X	X	X	X	X	X	X	X	X	
Dispense weight diary			X				X		X			X		X		
Collect/review weight diary				X	X	X	X	X	X	X	X	X	X	X	X	
ECG	X														X	X
Echocardiogram ^f	X															
Vital sign measurements	X		X		X		X		X			X		X	X	X
Physical exam	X		X		X		X		X			X		X	X	X
Pregnancy test for WOCBP ^g	X	X	X						X					X	X	X
Study drug administration				-----X-----												
Dispense study drug			X				X		X			X		X		
Collect study drug							X		X			X		X	X	
Telephone contact				X		X		X		X	X		X			
Adverse event collection			x ^h	X	X	X	X	X	X	X	X	X	X	X	X	X
Kidney biopsy ⁱ	X															
Fasting C-peptide level ^j	X															

Genetic testing ^k	X															
Assessment	Screen A ^a	Screen B ^b	Day 1 ^c	Wk 1 (Phone) Day 3±2	Wk 1 Day 7±3	Wk 2 (Phone) Day 10±2	Wk 2 Day 14±3	Wk 3 (Phone) Day 21±2	Wk 4 Day 28±3	Wk 4 (Phone) Day 31±2	Wk 5 (Phone) Day 38±2	Wk 6 Day 42±3	Wk 7 (Phone) Day 45±2	Wk 8 Day 56±3	Wk 12 or EoT ^d Day 84±3	Wk 16 or F/U Day 112±3
Clinical chemistry (incl. eGFR)	X	X	X		X		X		X			X		X	X	X
BNP and NT-proBNP	X		X		X		X		X			X		X	X	X
IGF-1 and serum ketones	X		X		X		X		X			X		X	X	X
Hematology	X		X				X		X			X		X	X	X
Urinalysis and microscopy	X		X				X		X			X		X	X	X
Urine collection for ACR ^e		X	X						X					X	X	X
██████████															X	X
██████████															X	X
Virus serology	X															
PK samples ^f															X	

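### SAP 12.2's any-time laboratory counts do not separate low magnesium already present at baseline from new cases on drug (minor)

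*SAP*

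**What the plan says.** SAP 12.2 plans, by cohort, the number and percentage of patients meeting a "pre-specified threshold level at any time during the study (Table 7) and 2) ULN thresholds at any time during the study (Table 8". Table 7 includes magnesium below 1.3 mEq/L. This is the protocol's own cut-off for hypomagnesaemia, "defined as serum magnesium less than 1.3 mEq/L (0.65 mmol/L" (Protocol 9.1.5). The section specifies no post-dose restriction, normal-baseline condition, baseline column or shift table for these counts.

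Magnesium belongs to the chemistry panel, whose list ends "lactate dehydrogenase (LDH), magnesium, chloride, bicarbonate, and GGT" (Protocol 9.10.20). The row "Clinical chemistry (incl. eGFR" in SAP Table 2 schedules that panel at Screen A, Screen B and Day 1 (before dosing), at Weeks 1, 2, 4, 6, 8 and 12, and at Week 16 off drug.

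The SAP ties other safety counts to dosing. Under 12.1.1, a treatment-emergent AE must begin or worsen from the first dose on. Under 12.5, ECG thresholds are counted by time point and overall while on drug, with separate QTcF increase-from-baseline rows.

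**The concern.** Safety is one of the two primary objectives and there is no control arm, so nothing in the table shows the background rate of low magnesium. A reader may naturally take the count as what happened on drug.

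Hypomagnesaemia is also an effect already associated with this drug. In earlier studies it "was reported as an AE for 15.5% of patients with CKD who also had type 2 diabetes who received bardoxolone methyl" (Protocol 5.1.2.5), and serum magnesium fell within the first 4 weeks. That makes it worth knowing whether a counted patient crossed the level after starting treatment or was below it beforehand. The rule as written does not distinguish the two.

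**Working it through.** The plan gives no figure for this count, so there is none to reproduce. The check has two parts.

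**1. Which Table 7 rows could already be met before dosing?** Compare each level with the entry criteria (Protocol 8.1 and 8.2).

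| Row | Table 7 level | Entry limit | Gap |
|---|---|---|---|
| ACR | > 3500 mg/g | ≤ 2500 mg/g at Screen B | 3500/2500 = 1.4-fold rise needed |
| ALT, AST | > 3 × ULN and higher | ≤ 1.5 × ULN at Screen A | 3/1.5 = 2-fold rise needed |
| BNP | > 200 pg/mL | > 200 pg/mL excluded at Screen A | none above at Screen A; a Day 1 value could be |
| Magnesium | < 1.3 mEq/L | no numeric limit | open |

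For magnesium, the only barrier at entry is the investigator's general discretion over abnormal laboratory values (Protocol 8.2). The combined transaminase row also requires ALT or AST above 3 × ULN, so it is protected in the same way.

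**2. How much could it matter?** One patient in a cohort of 25 is 1/25 = 4 percentage points. The expected number depends on:

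- n = 25 per cohort (Protocol 7.2).
- p0, the share below 1.3 mEq/L before dosing. The documents do not give it; assumed 0% to 8%.
- q, the share newly crossing among patients not low at baseline. The 15.5% AE rate is used as a stand-in. It is an AE rate rather than a laboratory rate, and it comes from type 2 diabetes, which is none of the four cohorts.
- r, the share of baseline-low patients who stay low after dosing. Assumed 0.5, with no source in the documents.

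Formulas:

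- All values counted: n × [p0 + (1 − p0) × q], of which n × p0 are pre-existing.
- Post-dose values only: n × [p0 × (r + (1 − r) × q) + (1 − p0) × q], of which n × p0 × r are persisting baseline cases.
- Chance that a cohort has at least one baseline-low patient: 1 − (1 − p0)^25.

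At p0 = 4%, counting all values gives 25 × [0.04 + 0.96 × 0.155] = 25 × 0.1888 = 4.72. Counting post-dose values gives 25 × [0.04 × 0.5775 + 0.1488] = 25 × 0.1719 = 4.30.

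| p0 | Chance of ≥ 1 | Count, all values | of which pre-existing | Count, post-dose | of which persisting |
|---|---|---|---|---|---|
| 0% | 0% | 3.9 | 0 | 3.9 | 0 |
| 2% | 40% | 4.3 | 0.5 | 4.1 | 0.25 |
| 4% | 64% | 4.7 | 1.0 | 4.3 | 0.5 |
| 8% | 88% | 5.6 | 2.0 | 4.7 | 1.0 |

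As a share of the count, pre-existing cases run from 0% to 2.0/5.57 = 36% if all values count, and from 0% to 1.0/4.72 = 21% if only post-dose values count. These figures illustrate the mechanism; they do not estimate it.

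**The case against.** The strongest reply is that the wording was probably meant as post-dose. The protocol starts study time at the first dose for AEs ("during the study (from time of administration of the first dose at the Day 1 visit", Protocol 11.2.1.1) and again for pregnancies (11.2.1.2). Protocol 11.6 asks for follow-up of abnormal laboratory results seen in the study, in a section whose collection period begins after the first dose. This stands as support for the post-dose reading, so a reader should not infer that screening values are certain to be counted. It does not settle the matter: the SAP never carries the definition into 12.2, and its Table 3 treats Screen A, Screen B and Day 1 as analysis visits. Nor does it remove the problem, since a patient low at baseline who stays low is counted on either reading.

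The second reply is that other outputs already answer the question. SAP 12.2 summarises chemistry at each scheduled time point, and SAP 7 includes the minimum, so a pre-dose minimum at or above 1.3 mEq/L would show that no summarised pre-dose value was low. Change from baseline is summarised, and "Laboratory results that are above or below normal limits will be flagged in the listings". Treatment-emergent AE tables isolate new or worsened hypomagnesaemia that was reported as an AE. These are real but partial checks. The minimum does not say how many patients were low or who they were. Mean change does not show crossings. The listings flag normal limits rather than the Table 7 level and must be sorted by hand. Laboratory changes become AEs only when judged clinically significant (Protocol 11.6).

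Third, the error runs one way: it can overstate hypomagnesaemia but cannot hide a new case. That is correct, and it is a main reason the point is minor.

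A reader might also infer that ALT, AST and bilirubin are exposed through Table 8, because entry allows values up to 1.5 × ULN. The documents do not support that as a finding. Table 8 is titled "Pre-Specified Upper Limit of Normal (ULN) Levels for Laboratory Parameters" and can be read as supplying the reference limits for the multiples in Table 7. Nothing in it sets out a count above 1 × ULN.

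**Conclusion.** The point holds as a minor one, confined to the magnesium row of Table 7. As written, the rule can mix low values present at baseline with new cases, and it does so on either reading of the study period.

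The size is unknown and may be zero. What the documents support is the unit: 4 percentage points per baseline-low patient counted without a new crossing in a cohort of 25, always upwards. The expected counts above rest on an assumed baseline prevalence of 0% to 8%, an assumed persistence of one half, and an AE rate borrowed from another population.

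It would be tempting to conclude that the hypomagnesaemia rate will be materially inflated, or that the laboratory threshold tables are unreliable in general. Neither follows: there is no prevalence on which to base the first, and the entry criteria largely protect the other rows. The table is descriptive, no test, dosing rule or stopping rule uses the count, and the eGFR analysis is untouched.

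**What to change.** In SAP 12.2, state that the Table 7 counts use values obtained after the first dose, with all dosed patients kept in the count. For magnesium, show the count split by whether the baseline value was below 1.3 mEq/L, or give a shift table of baseline against the worst post-dose value. The default baseline in SAP 7.2 (last non-missing value before dosing) already serves for this.

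The cost is a sentence of SAP text and one small extra table per cohort, from data already collected. Because no patient is dropped, worsening in someone who entered low remains visible.
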